5.7. Administration

The study intervention will be administered in an outpatient setting. The research pharmacy will dispense one dose of CAP to a member of the study team, who will reconstitute the CAP powder in 10-12 ounces of room temperature water and provide it to the participant for oral consumption. One dose will be administered at each study visit in a random order.

5.8. Modification to study intervention

There will be no modifications to the study intervention during the study unless there are adverse events are noted and recommendations are made by the study's Independent Monitoring Committee (IMC).

5.9. Criteria for intervention discontinuation and stopping guidelines

Participants will be advised during the informed consent process that they have the right to permanently discontinue the *Centella asiatica* product and/or withdraw from the study at any time without negative repercussions. Participants will also be counseled during the consent process that they may be withdrawn from the study at the discretion of the Principal Investigator or designees. A participant may discontinue and/or withdraw and/or be withdrawn from the study for the following reasons:

Administrative:

- 1) Withdrawal of participant consent
- 2) Request of site investigator or designees
- 3) Request of primary care physician
- 4) Non-compliance
- 5) Protocol deviation
- 6) Premature termination of the study

Adverse event (AE)/experience:

- 1) Worsening of pre-existing disease
- 2) Intercurrent illness
- 3) Death
- 4) Major/clinically significant alteration in laboratory values or biometric assessments after beginning product
- 5) Other AE
- 6) Other reasons concerning the participant's health or well-being

The study will be terminated if two participants terminate due to intervention-related adverse events. Severe adverse events will be reviewed immediately by the Principal Investigator, clinical investigators and the Independent Monitoring Committee (IMC) to determine if severity and relatedness warrant termination of the study.

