6.10. Tolerability and safety assessments

Visit 1 and 2 tolerability phone assessment: Participants will be telephoned the day following each study visit to assess for delayed adverse events and/or complications from the intravenous catheter placement using interviews and a standardized multi-system adverse events questionnaire (Figure 3, Table 5). Participants will be instructed to contact a study clinician if they experience any reactions following the phone assessment, and prior to their second study visit or one-week exit interview.

Exit interview tolerability assessment: Participants will be telephoned one week following the completion of their second study visit, or first study visit if they elect to drop out of the study, to assess for delayed adverse events and/or complications from the intravenous catheter placement using interviews and a standardized multi-system adverse events questionnaire (Figure 3, Table 5).

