7. PROVISIONS TO MONITOR THE DATA TO ENSURE SUBJECT SAFETY

Adverse event (AE) monitoring will occur in “real time” using a standardized Adverse Event Monitoring Form and reviewed weekly by the principal ([name]) and clinical ([name]) investigators. This form is a ninety-one point multi-system questionnaire that assesses all organ systems (eyes/ears/nose/throat, gastrointestinal, neurological/ musculoskeletal, psychological/general, cardiopulmonary, skin, genitourinary and whole body systems). It will be completed at the screening visit in order to collect data on any/all pre-existing symptoms and their severity, and will serve as baseline data to determine attribution to the study intervention. The Adverse Event Monitoring Form will be administered in person at the beginning and end of Visits 1 and 2, via telephone the day following Visit 1 and 2, and by telephone one week after Visit 2, to assess for acute and delayed adverse events. Electrocardiograms will be performed just prior to administration of *Centella asiatica* product and six hours after intervention to monitor for adverse events. This time point has been selected based on prior pharmacokinetic literature on *Centella asiatica* triterpenes and from our murine studies which suggest that at 6 hours, the bioactive triterpenes should have reached maximum concentration and the caffeoylquinic acids are beyond their time of maximum concentration. This is also to allow for the collection of the ECG to be feasible given the frequent timing and short intervals between blood sample collection earlier in the experiment. A comprehensive metabolic panel (CMP) will be measured at baseline of each study visit and at 10 hours after CAP administration to assess for liver or kidney toxicity. This time point was selected to allow for markers of toxicity to develop if present, and for logistical reasons to allow adequate time for sample collection, processing and transfer to the OHSU Core Laboratory for analysis within the 10 hour time frame of the experiment.

Participants will be reminded and encouraged during clinic visits to contact a study clinician if a moderate or serious AE occurs. Participants will be given a telephone number they can call at any time to report potential adverse effects. All severe AEs will immediately be reported to the Independent Monitoring Committee (IMC) and the OHSU IRB by the study principal investigator.

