7.3. Plan for review and reporting

The IMC will meet biannually to study un-blinded AE data coded by organ system, and on an ad-hoc basis as necessary, based on the cited reporting of severe AEs and continuing reviews to OHSU's IRB. Should it be determined that the protocol need to be amended as a result of data review, the principal investigator will submit a protocol amendment to the sponsor (NCCIH) for approval. Once approval is obtained from the sponsor, the amendment will be submitted to the OHSU IRB and monitoring body and the amendment approved prior to study amendment implementation, unless immediate implementation is required to protect the safety of the study participants. In such a case, the protocol amendment will be immediately implemented and the sponsor, OHSU IRB and IMC will be notified directly after protocol amendment implementation.

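### The numeric stopping rule counts participants who terminate, so a related discontinuation-level event after the second and last dose does not count unless that participant leaves the study before the day-7 call

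*Combined protocol and SAP*

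**What the plan says.** The rule in section 5.9 reads: "The study will be terminated if two participants terminate due to intervention-related adverse events". The unit counted is a participant who terminates, not a participant who has a related event. The same section sets out how participants may leave: "A participant may discontinue and/or withdraw and/or be withdrawn from the study for the following reasons". One listed adverse-event reason is "Major/clinically significant alteration in laboratory values or biometric assessments after beginning product". That list applies after either dose.

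The schedule is short. Section 5.7 states "One dose will be administered at each study visit in a random order", and there are two dosing visits. After the Visit 2 dose, what remains is the rest of the 10-hour visit, a next-day call, and the exit call in section 6.10: "Participants will be telephoned one week following the completion of their second study visit". Section 6.2 describes rolling enrolment, and section 6.11 allows seven months for recruitment and data collection.

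Other safeguards apply after either dose:
- Section 5.9 requires immediate review of severe events by the investigators and the IMC.
- Section 7 describes ongoing monitoring "using a standardized Adverse Event Monitoring Form and reviewed weekly by the principal" and clinical investigators.
- Section 7.3 states "The IMC will meet biannually to study un-blinded AE data coded by organ system, and on an ad-hoc basis as necessary".
- Section 5.8 allows the intervention to be modified on IMC recommendations.

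None of these states a number of events. Section 7.2 refers to an IMC charter that is not part of the document.

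**The concern.** The same finding is treated differently depending on which visit it follows. Suppose the 10-hour metabolic panel shows a clinically significant liver-enzyme rise judged related to the product. After dose 1, the natural response is to withhold dose 2; the participant discontinues and adds one to the count. After dose 2, the natural response is to follow the participant through the two remaining calls. That participant completes, and the count does not move. With order randomised, about half of the 4 g doses fall where the rule is least likely to register an event.

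Section 2.5.4 says that no human safety data exist for concentrated water extracts at 2 g and 4 g, and it names possible liver toxicity. A rule meant to stop automatically at two affected participants could therefore stay silent with two affected and others still to be dosed. The decision would then rest on judgement.

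**Working it through.** **What the plan gives.** There is no stated event rate, trigger probability or other operating characteristic for the rule, so there is no plan figure to reproduce.

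**Inputs from the documents.** 8 participants (4.1); two doses each, so 16 planned doses; order randomised towards equal numbers (5.6), taken as 4 participants with 4 g first and 4 with 4 g second; threshold of 2 participants (5.9).

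**Assumptions.** Discontinuation-level related events occur only at 4 g, with probability *p* per dose, independently. Every such event after dose 1 leads to termination. A share *w* of those after dose 2 leads to withdrawal, with *w* from 0 to 0.5. Setting *w* = 1 gives the rule that counts events after either dose.

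**Formula.** With *a* = *p* for the four 4 g-first participants and *b* = *pw* for the four 4 g-second participants:

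- P(0) = (1−a)⁴(1−b)⁴
- P(1) = 4a(1−a)³(1−b)⁴ + 4b(1−b)³(1−a)⁴
- P(trigger) = 1 − P(0) − P(1)

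**At p = 0.05:**

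- *w* = 0: 1 − 0.81451 − 0.17147 = 0.014
- *w* = 0.5: 1 − 0.73606 − 0.23045 = 0.033
- *w* = 1: 1 − 0.66342 − 0.27933 = 0.057

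| Assumed *p* per 4 g dose | As written (*w* = 0 to 0.5) | Events after either dose count |
|---|---|---|
| 1% | 0.06-0.15% | 0.27% |
| 5% | 1.4-3.3% | 5.7% |
| 15% | 11-22% | 34% |
| 25% | 26-46% | 63% |

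**How far the model matters.** If both doses carried the same 5% risk and no dose-2 event led to withdrawal, the comparison would be P(at least 2 of 8) at 0.05, which is 5.7%, against P(at least 2 of 8) at 1 − 0.95² = 0.0975, which is 18.0%.

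**Where 5% comes from.** Section 2.5.1 reports one withdrawal for liver enzymes on CAST, with adverse events in 80% of that arm, 56% of placebo, and 29 of 43 overall. Arms of 20 and 23 fit (16/20 = 80%; 13/23 = 56.5%; 16 + 13 = 29), giving about 1 in 20. That was a different product taken daily for up to 52 weeks, and all events were graded minor. It is the nearest figure in the documents, but it does not estimate the risk of one 4 g dose.

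**Extra doses.** Simulation of 200,000 trials: 3 weeks between visits, no second dose after a dose-1 event, no discretionary stop. The result is mean doses under the rule as written minus mean doses under the event-based rule; ranges run over *w* = 0.5 to 0.

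| Scenario | 5% | 15% | 25% |
|---|---|---|---|
| Starts 3.5 weeks apart, event known in 1 day | 0.1-0.2 | 0.6-1.2 | 1.2-2.4 |
| Starts 1 week apart, 1-week lag, dose due at the moment of stopping still given | 0.05-0.1 | 0.3-0.6 | 0.6-1.2 |
| As above, that dose withheld | 0.08-0.15 | 0.5-0.9 | 0.8-1.7 |

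The last two rows differ because one-week starts and a one-week lag put the stop exactly on dosing days.

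**The case against.** The strongest reply is that the study is already protected. It has one site and eight participants. Investigators review adverse events weekly, a single severe event brings immediate review by investigators and IMC, and the IMC can meet ad hoc. Two related events of this kind would be hard to overlook. Section 5.9 also lets the investigator withdraw a participant at any point up to the exit call, and such a withdrawal would count. The term for leaving is undefined, and the charter may contain a count of its own. The only rate near 5% comes from a different product and regimen; at 1% per 4 g dose the gap is negligible, with under 0.01 extra doses.

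Most of this stands, and it limits the point. A reader might infer that an event after dose 2 can never count, or that such events would go unreviewed. The documents support neither reading. What the reply does not do is repair the count. The severe-event review does not reach non-severe events, the other safeguards are matters of judgement, and withdrawing someone with no dose left is optional.

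The reply is also right that the 5.9 list ends in broad items covering any other adverse event or health reason. A fix that merely pointed to the list would be loose.

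**Conclusion.** The point holds as a minor gap in wording. On the text of 5.9, a related, non-severe, discontinuation-level event after the second dose does not count unless the participant leaves before the day-7 call. Two such events need not trigger the rule while rolling enrolment leaves others undosed. This follows from the wording and the two-dose schedule, not from any assumed rate.

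Its size depends entirely on assumptions: the event rate, which dose carries the risk, and how often participants withdraw after dose 2. At 5% per 4 g dose the effect is small, with a trigger probability of 1.4-3.3% against 5.7% and about 0.05-0.2 extra doses of 16. The 15% and 25% rows are illustrative and have no support in the documents; a reader should not infer that such rates are expected. Nor are the dose figures upper limits. They ignore discretionary stopping, which would lower them, but they also move with enrolment spacing, reporting lag and the handling of a dose due at the moment of stopping. Whether the IMC charter already closes the gap cannot be judged from the documents.

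**What to change.** Reword the rule in 5.9 so that the study is terminated if two participants have an intervention-related adverse event, attributed under 7.1, that a study clinician blinded to dose judges major or clinically significant enough that a further dose would be withheld. Events after either dose and through the day-7 call count, whether or not the participant leaves the study. State that the mild, transient gastrointestinal symptoms expected in 8.1 do not count. Align the IMC charter if it repeats the rule.

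The cost is one sentence, one yes/no item on the adverse event form, and possibly a charter edit. There are three downsides. After dose 2 the clinician judges a dose that is no longer due, which is a hypothetical call. The rule triggers somewhat more often (5.7% instead of 1.4-3.3% at the assumed 5% risk). An early stop could leave fewer than the 7 participants that section 10.8 requires for AUC.

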5.10. Concomitant interventions

5.10.1. Allowed interventions: diphenhydramine, temporary use of sedatives for sleep (such as Ambien), probiotic supplements, non-plant based laxatives such as magnesium citrate or milk of magnesia, gastroesophageal reflux disorder medications such as antacids (non-flavored), central nervous system active medications that have been stable for greater than two months, analgesics

5.10.2. Required interventions: cholinesterase inhibitors therapy for the treatment of cognitive decline. The dose needs to be stable for a minimum of 12 weeks prior to study enrollment.

5.10.3. Prohibited interventions: sedatives (except those used occasionally for sleep), central nervous system active medications that have not been stable for two months (including beta blockers, cimetidine, SSRIs, SNRIs), anticoagulants (i.e. Warfarin), investigational drugs used within five half-lives of baseline visit, systemic corticosteroids, neuroleptics, anti-Parkinsonian agents, narcotic analgesics, nicotine (tobacco, patches, gum, lozenges, etc.), *Cannabis sativa* (herb or edibles), any over the counter or prescribed products containing plant extracts such as herbal supplements, plant based over the counter vitamin supplements, plant based over the counter protein powder supplements

6. SCREENING AND STUDY ACTIVITIES

6.1. Candidate identification

We require equal numbers of male and female elderly subjects (age 65-85). These would include 8 individuals with amnesic mild cognitive impairment (MCI) or mild Alzheimer's disease (AD).

We will utilize the following resources available at OHSU to identify potential subjects:

- Oregon Alzheimer Disease Center (OADC) registry of subjects enrolled in a longitudinal study;
- NeuroNEXT database (an NINDS initiative to conduct/foster exploratory trials in neurological conditions). [name] (Co-PI) has access;
- OHSU's patient database EPIC using the "Cognos" searching tool.

The table below gives the numbers of subjects that *prima facie* would qualify for our study from these sources.

Table 4. Recruitment resources

Resource	Number of mild AD subjects ^[SEP] Age 65-85
OCTRI research volunteer repository Research Match	0 with known MCI/AD
OADC subjects registered in an NIA funded longitudinal study and who have consented to being approached for clinical trials. Mild AD or MCI (age 65-85; CDR 0.5-1 and MMSE 20-28): ^[SEP] 38 women, 20 men, of which 13 women, 11 men are OHSU patients.	38 women and 20 men, of which 10 women and 6 men are already OHSU patients. CDR 0.5 to 1 MMSE 20-25
NIH/NINDS Neuronext database of subjects interested in taking part in dementia research	11 women and 10 men who registered with clinically confirmed diagnoses of MCI
Data from Cognos search of EPIC ^[SEP] Feasibility of in-clinic recruitment for OHSU's Layton Center for Alzheimer's and Aging based on visits over the last 12 months	40 women and 37 men with confirmed MCI were seen at OHSU in the last 12 month
Totals assuming no overlap between recruitment tools	89 women, and 67 men

If we require additional subjects beyond the number we can recruit from these sources, we will use additional methods. For example, the Oregon Clinical and Translational Research Institute at OHSU also provides other recruitment tools such as "Research Data Warehouse" and "Cohort Discovery".

6.2. Recruitment

Participants will be enrolled on a rolling basis until the desired number of participants is achieved. Potential participants available through the above sources will be mailed a study advertisement describing the study and requesting they call if they are interested in participation. The study will be advertised using fliers in out-patient OHSU clinics, other regional hospitals within traveling distance to OHSU, local retirement communities/elder care facilities and an online posting in the March Wellness "March Stride" e-mail newsletter. In addition, it will be advertised using the NIH Clinical Trials website, local newspapers and radio announcements. We will also advertise through online social media platforms, such as targeted Facebook ads. We may also recruit by obtaining physician referrals from providers outside of OHSU using IRB approved recruitment materials. It will be emphasized that participation in the study is completely voluntary. Copies of all advertisements and non-OHSU physician referral request letters will be submitted for IRB approval.

6.3. Incentives

Participants will be given the option of complimentary transportation by taxi to and from their study visits (up to \$50 per visit) or a parking permit for each study visit. They will not be provided with transportation for screening visits. To compensate them for their time and effort, participants will receive \$80 for completion of the study via the ClinCard. Prorated amounts of \$40 per study visit will be implemented for participants who do not complete the study and provided using the above card at the end of the first study visit. While not a direct incentive, participants will be provided with three complete meals and snacks during each study visit that comply with a low plant diet.

6.4. Phone screening

Potential participants will be screened over the phone by a member of the study team, primarily the study coordinator, prior to coming in for the in-person screening visit. A standardized

telephone script will be used and will be submitted for IRB approval. The script will ask the study participant basic questions about eligibility and provide necessary details about the study purpose, duration of visits, number of visits and major procedures. Study personnel conducting the phone screening will then ask to talk to the participant's designated study partner to discuss the study in more detail and ask detailed eligibility questions including medical history. The telephone screening will take approximately 10-15 minutes. Potential participants that meet eligibility criteria over the phone will be scheduled for a screening visit with their study partner.

6.5. Consent process

Participants: To ensure full comprehension of all aspects of their participation in the study, all potential participants will be mailed a copy of the IRB approved consent and HIPAA form prior to their in-person screening visit. They will be instructed to review the form ahead of time but not to sign it until the visit. All in-person screening visits and consenting will occur in a Clinical and Translational Research Center's outpatient room. At the in-person screening visit, a study clinician will review the single consent/HIPAA form that describes both the screening and study procedures and then will ask the participant and ARR to describe key points in the form (e.g. purpose of study, dietary requirements, length of study) before signing. A physical copy of their consent form will be provided to each participant and kept in the affiliated study folders to be made available as necessary to an Independent Monitoring Committee or the OHSU IRB. To ensure ongoing consent, participants and their LAR will be called three days prior to their second study visit to ask if they wish to continue their participation in the study. This will be documented in the participant's instance of REDCap. Appropriate language will be included in the consent form to avoid coercion. We will underscore that they can decline to participate at any point in the study, even if they have signed the consent form, and it will not impact their participation in future research trials or health care.

Study partner: To ensure full comprehension of all aspects of their participation as a study partner in the study, all potential study partners will be consented in the screening visit with their participant. All in-person screening visits and consenting will occur in a Clinical and Translational Research Center's outpatient room. At the in-person screening visit, a study clinician will review the single consent/HIPAA form that describes both the screening and study procedures and then will ask the study partner to describe key points in the form (e.g. purpose of study, dietary requirements, length of study) before signing. A physical copy of their consent form will be provided to each study partner and kept in the affiliated study folders to be made available as necessary to an Independent Monitoring Committee or the OHSU IRB. To ensure ongoing consent, the study partner will be called three days prior to the second study visit to ask if they wish to continue their participation in the study. This will be documented in the participant's instance of REDCap. Appropriate language will be included in the consent form to avoid coercion. We will underscore that they can decline to participate at any point in the study, even if they have signed the consent form, and it will not impact their participation in future research trials or health care.

